6.5.2 Unblinding during the clinical trial

Emergency un-blinding during the clinical trial may be required for therapeutic or for regulatory reasons (e.g. for expedited safety reporting).

A blind-break system will be available for Investigators. At the clinical trial center, the blinded label containing the identification of the assigned study drug(s) will be revealed in emergency situations only. In such an emergency, the Investigator will only break the blind for the subject involved.

Treatment identification for emergency purposes will be possible with "unblinding envelopes", stating the treatment number, investigational product identification, batch number and investigational product expiration date, as applicable.

Protocol N° RD.03.SPR.113322

version Final dated 10-FEB-2017

Page 56 of 106 CONFIDENTIAL

The investigator must notify the sponsor immediately in the event of such an emergency (see contact details in Section 8.2.2). If possible, the investigator should notify the sponsor before breaking the blind in order to discuss this decision with the sponsor. The investigator is required to document each case of emergency un-blinding on the appropriate form (provided by the Sponsor) and send the completed form to the sponsor immediately.

7. EFFICACY AND SAFETY ASSESSMENT

Clinical evaluations should be performed by the same evaluator (investigator or designee) throughout the clinical trial.

If it is not possible to use the same evaluator to follow a subject, then evaluations should overlap for at least one visit in order to examine the subject together and discuss findings. This should be documented in medical source documents.

7.1 EFFICACY ASSESSMENTS

7.1.1 Inflammatory Lesion Count

The evaluator will perform inflammatory lesion count on facial papules and pustules of rosacea at baseline and then at each visit.

Inflammatory lesions are defined as follows:

- Papule A small, solid elevation less than one centimeter in diameter
- Pustule A small, circumscribed elevation of the skin, which contains yellow white exudates.

Papules and pustules will be counted separately on each of the five facial regions (forehead, chin, nose, right cheek and left cheek). **Nodules** (defined as a circumscribed, elevated, solid lesion more than 1.0 cm in diameter with palpable depth) **will not be included in the count of inflammatory lesions**, and subjects are not eligible if they have more than 2 nodules on the face at screening/baseline visit.

7.1.2 Clinician's Erythema Assessment (CEA)

The evaluator will assess the subject's diffuse persistent facial erythema of rosacea by performing a static ("snap shot") evaluation of erythema severity, at a social distance of approximately 50 cm, using CEA at each visit. The evaluator should make no reference to previous assessments when evaluating the subject's erythema of rosacea and CEA must be evaluated after the inflammatory lesion count.

Protocol N° RD.03.SPR.113322

version Final dated 10-FEB-2017

Page 57 of 106 CONFIDENTIAL

Grade	Description
0	Clear skin with no signs of erythema
1	Almost clear; slight redness
2	Mild erythema; definite redness
3	Moderate erythema; marked redness
4	Severe erythema; fiery redness

7.1.3 Investigator's Global Assessment (IGA)

The evaluator will assess the subject's rosacea at each visit by performing a static ("snap-shot") evaluation, at a social distance of approximately 50 cm, using IGA score. No reference to previous visits should be made by the evaluator. A subject must have an IGA of 4 (severe) to be eligible for the study.

Grade	Score	Clinical Description
Clear	0	No inflammatory lesions present, no erythema
Almost Clear	1	Very few small papules/pustules, very mild erythema present
Mild	2	Few small papules/pustules, mild erythema,
Moderate	3	Several small or large papules/pustules, moderate erythema,
Severe	4	Numerous small and/or large papules/pustules, severe erythema,

7.1.4 Stinging/Burning sensation

The evaluator will record the severity of subject's facial stinging/burning sensation (a prickling pain sensation) during the last 24h at each visit.

Protocol N° RD.03.SPR.113322

version Final dated 10-FEB-2017

Page 58 of 106 CONFIDENTIAL

Grade	Score	Clinical Description
None	0	No stinging/burning
Mild	1	Slight warm, tingling/stinging sensation; not really bothersome
Moderate	2	Definite warm, tingling/stinging sensation that is somewhat bothersome
Severe	3	Hot, tingling/stinging sensation that has caused definite discomfort

7.1.5 Ocular Signs and Symptoms

Ocular manifestations will be evaluated by the Evaluator after discussion with the subject. The Evaluator may identify ocular manifestations by looking for tearing, redness of bulbar and/or palpebral conjunctivae, telangiectasia of conjunctiva and lid margin, lid or periocular erythema, or styes, and by inquiring about symptoms of foreign-body sensation, gritty feeling, burning, stinging, itching, dryness, light sensitivity, blurred vision, or decreased visual acuity.

Grading of ophthalmological abnormalities in ocular rosacea will be based on clinical opinion of dermatologist and evaluated at each visit using the below scale.

Grade	Score	Clinical Description
None	0	No ocular sign/symptom
Mild	1	Mild blepharitis with lid margin telangiectasia
Mild-Moderate	2	Blepharoconjunctivitis
Moderate-Severe	3	Blepharo-keratoconjunctivitis
Severe	4	Sclerokeratitis, anterior uveitis

7.1.6 Flushing

At baseline, Investigator will record in medical history the frequency (number) of flushing as reported by subject for the previous week before baseline visit and the corresponding average severity by grading as mild, moderate or severe.

Protocol N° RD.03.SPR.113322

version Final dated 10-FEB-2017

Page 59 of 106 CONFIDENTIAL

During the study, the number of weekly flushing and the average severity will be recorded from Subject's diary where subject will be asked to report each day the flushing episodes. Investigator or designee will have to check with subject for diary completeness at each visit and report flushing information in the eCRF.

Protocol N° RD.03.SPR.113322

version Final dated 10-FEB-2017

Page 60 of 106 CONFIDENTIAL

7.1.7 Subject's Global Improvement in Rosacea

The subject will evaluate his/her improvement in rosacea at last visit, compared with his/her rosacea condition before the study.

0	Complete improvement	All signs and symptoms of disease have resolved
ľ	Complete improvement	(100% improvement from Baseline)
1	Excellent Improvement	Nearly all signs and symptoms cleared
		(90% improvement from Baseline). Only minimal residual signs and symptoms remain
2	Very good Improvement	Majority of the signs and symptoms have resolved
		(about 75% improvement from Baseline)
3	Good Improvement	Significant improvement, but many signs and symptoms remain (about 50% improvement from Baseline)
4	Minimal improvement	Slight overall improvement, but not clinically significant(about 25% improvement from Baseline)
5	No Change	Overall severity similar from Baseline
6	Worse	Worse than Baseline

Protocol N° RD.03.SPR.113322

version Final dated 10-FEB-2017

Page 61 of 106 CONFIDENTIAL

7.2 SAFETY ASSESSMENTS

A safety assessment will be conducted for all subjects at the screening/baseline visit (from the Informed consent signature) and every subsequent visit. The safety parameters and AEs are to be recorded as specified in section 7.2.1.

7.2.1 Adverse Events

Adverse events (AEs) are to be monitored throughout the course of the clinical trial. All AEs occurring after the subject signs the informed consent should be recorded on the AE form on the eCRF.

All AEs are to be reported on an Adverse Event Form of the eCRF with complete information as required. If AEs occur, the main concern will be the safety of the subject. At the time of the ICF signature, each subject must be provided with the name and telephone number of clinical trial center personnel for reporting AEs and medical emergencies.

All clinical medical events, whether observed by the investigator or reported by the subject and whether or not thought to be related to the study drug will be considered AEs. Assessment of seriousness, severity and causality will be based on specific definitions. If the subject discontinues due to an AE, both the AE Form and the Exit Form should be completed.

Subjects reporting a worsening of rosacea (worsening of any signs and symptoms of rosacea including but not limited to inflammatory lesions, persistent erythema and flushing) will be evaluated in detail. This includes the onset, duration and outcomes of those events, as well as a complete history and potential triggers of the concerned signs and symptoms of rosacea.

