The approval of Ivermectin 1% cream (FDA, 2015) for the treatment of the inflammatory lesions of rosacea was based upon two identically-designed large vehicle-controlled Phase 3 randomized trials that demonstrated efficacy and safety in adults with moderate to severe papulopustular rosacea on a 12-week treatment period. In both studies, a greater proportion of subjects in the IVM 1% group achieved treatment success. Ivermectin was superior to vehicle in terms of reduction from baseline in inflammatory lesion counts (76% and 75% versus 50% for both vehicle groups, respectively)^{1.13}. For Doxycycline the two placebocontrolled pivotal phase 3 trials evaluated the efficacy and safety of doxycycline 40 mg modified release (MR) once daily versus placebo in participants with moderate to severe rosacea. These participants had 10 to 40 papules and pustules and moderate to severe erythema and telangiectasia. Both studies showed marked reductions in the number of inflammatory lesions compared with placebo. Treatment with doxycycline 40 mg MR significantly reduced the number of lesions from the first follow-up assessment at 3 weeks throughout the entire 16-week study compared with placebo (P≤ 0.005). Study by Sanchez et al. 1.14 using doxycycline with metronidazole versus metronidazole alone did demonstrate in moderate to severe rosacea that adjunctive use of sub-antimicrobial dose doxycycline significantly reduced the clinical signs of rosacea compared with metronidazole alone 1.6. Based on the complementary mechanism of action of doxycycline MR and ivermectin^{1.10}, a scientific rationale to assess the combined therapy targeting inflammatory lesions in severe rosacea is planned. Topical ivermectin cream is a promising first-line treatment to target the inflammatory lesions of rosacea, which can be used in combination with systemic doxycycline modified-release as per the recent Canadian Rosacea guideline 1.15 to provide an optimal treatment approach considering all inflammatory pathways involved in rosacea with inflammatory lesions.

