4.4 PROCEDURES / REASONS FOR DISCONTINUATION

An Investigator may decide to discontinue a subject from the clinical trial for safety reasons.

Although the importance of completing the entire clinical trial should be explained to the subject by the clinical trial personnel, any subject is free to discontinue his/her participation in this clinical trial at any time and for whatever reason, specified or unspecified, and without prejudice.

Subjects who discontinue the clinical trial prematurely should be fully evaluated, whenever possible.

The procedures designated for the early termination visit will be completed for all premature discontinuation subjects. The appropriate eCRF pages for the next scheduled visit should be completed.

For all subjects who prematurely discontinue the clinical trial, the reason must be carefully documented by the investigator on the Exit Form, and, if applicable, on the Adverse Event Form for discontinuation due to an AE.

A subject who has been randomized and assigned a kit number cannot be replaced by another subject if he/she discontinues the clinical trial for any reason.

In the case of early termination, the investigator should ensure that the subject receives appropriate therapy for his/her condition.

GALDERMA R&D may also decide to prematurely terminate or suspend the clinical trial or the participation of a subject in the clinical trial.

All data gathered on the subject prior to termination will be made available to GALDERMA R&D.

Protocol N° RD.03.SPR.113322

version Final dated 10-FEB-2017

Page 39 of 106 CONFIDENTIAL

Reasons for clinical trial completion/discontinuation, as listed on the Exit Form of the CRF are described below:

Normal Study Completion	Subject completes the clinical trial as planned in protocol.
Pregnancy	Withdraw the subject from the clinical trial following the procedure described in the protocol section 8.3
Adverse Event	Complete CRF Adverse Event Form.
Withdrawal by subject	Includes consent withdrawal, subject relocation, schedule conflicts, etc Does not include AE Explain the reason for withdrawal in the comments section of the CRF Exit Form.
Protocol Violation	Explain the violation in the comments section of the CRF Exit Form
Lost to Follow-up	Confirm with 2 documented phone calls and a certified letter (delivery receipt requested) without response. Explain in the comments section of the CRF Exit Form.

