9.2 SAMPLE SIZE DETERMINATION

9.2.1 Historical data and assumptions

No previous study exists associating Ivermectin 1% cream and Doxycycline MR. Therefore, this sample size was calculated using the results (% change from baseline in inflammatory lesion counts at Week 12) of previous studies on subjects treated with:

- Ivermectin 1% cream alone, which showed a standard deviation (SD) between 25.4% to 39.9% (with a mean around 35%).
- Doxycycline MR alone, which showed a minimum difference of 26% at Week 12, vs. Placebo

Using this historical data, we can assume that the difference between the association (Ivermectin + Doxycycline MR) and Ivermectin will be at least of 15% with a SD of 35%.

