9.2.2 Sample size calculation

With the assumptions mentioned above, a total of 114 evaluable subjects per group will be required to demonstrate at least 15% difference at Week 12, with 90% power. To allow a 15% rate of subjects excluded from analysis (drop out, lost to follow-up, etc.) at Week 12, 135 subjects per group (270 in total) are to be enrolled.

Protocol N° RD.03.SPR.113322

version Final dated 10-FEB-2017

Page 78 of 106 CONFIDENTIAL

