6. STATISTICAL METHODS AND DATA CONSIDERATIONS

SAS version 9.3 will be used for all analyses. All tests will be two-sided and significance will be declared at a 0.05 level.

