8. TABLE SHELLS

14.1. Study Subjects

14.1.1. Conduct of the study

Table 1. Enrolment by analysis center and investigational site (ITT)

	IVM + Doxycycline (N=xxx)	IVM + Vehicle (N=xxx)	Total (N=xxx)
Analysis-Center 1 (n,%) Center 1 (n,%)			
Analysis-Center 2 (n,%)			

Table 2.1. Subjects who discontinued study and reason for discontinuation (ITT)

	IVM + Doxycycline	IVM + Vehicle	Total
	(N=xxx)	(N=xxx)	(N=xxx)
Randomized			
Normal study completion n (%)			
Premature discontinuation n (%)			
Lack of efficacy n (%)			
Adverse event n (%)			

Table 2.2. Listing of subjects who discontinued treatment and reason for discontinuation (ITT)

 $(Include: treatment, investigator\ number, subject\ number\ and\ reason\ for\ discontinuation)$

Table 3. Adherence to the visit schedule in days (ITT)

	IVM + Doxycycline	IVM + Vehicle	Total
Nb of days between baseline visit and week 4 visit			
N			
Mean±SD			
Median			
(Min,Max)			
Nb of days between baseline visit and week 12 visit			
N			
Mean±SD			
Median			
(Min,Max)			
Nb of days between baseline visit and last visit			
N			
Mean±SD			
Median			
(Min,Max)			

Table 4.1. Major protocol deviations (ITT)

	IVM +	Doxycycline	IVM +	- Vehicle		Total
eg:	N.	% subj.	N	% subj.	N	% subj.
AT LEAST ONE MAJOR DEVIATION						
No post-Baseline data						
No study medication dispensed						

A subject may have several major protocol deviations

Numbers in columns cannot be added because a given subject may have reported more than one deviation.

Table 4.2. Listing of subjects with Major protocol deviations (ITT)

(Include: treatment, investigator number, subject number, reason and detail of deviations)

Table 5. Data sets analyzed

	IVM + Doxycycline	IVM + Vehicle	Total
Intent to treat population (ITT) n(%)			
Per Protocol population (PP) n(%)*			
Safety population (APT) n(%)*			

^{*} Denominator is the number of subjects in the Intent to treat population

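### Permanently stopping study product is not separated from leaving the trial, so no Week 12 lesion count is scheduled after an adverse-event exit and an earlier count takes its place

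*Protocol*

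**What the plan says.** **Leaving.** Protocol 7.2.1 sends an adverse-event discontinuation to the Exit Form: "If the subject discontinues due to an AE, both the AE Form and the Exit Form should be completed". Section 4.4 describes that form as recording why a subject completed or left the trial, and adverse event is one of its listed reasons. The same section adds: "The procedures designated for the early termination visit will be completed for all premature discontinuation subjects". Section 5.5.2 makes these the last-visit procedures, which include a lesion count (5.5.3, item 3). Section 4.4 has the data entered on the eCRF pages of the next scheduled visit. No section of either document schedules a later count for a subject who has permanently stopped.

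**Analysis.** The primary variable is percent change in inflammatory lesion count at Week 12 (Protocol 9.1.1.1; SAP 4.1.1), tested on ITT, meaning everyone assigned a kit number. Missing counts are filled by LOCF, or by baseline if nothing later exists (Protocol 9.1.2.4; SAP 5.4). The stated robustness check is the PP analysis (Protocol 9.1.4; SAP 6.3.1). Protocol 9.1.2.1 gives an unavailable efficacy assessment as an example of a major deviation.

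**Labels.** SAP Table 2.1 counts subjects who left the study. Table 2.2 lists those who stopped treatment, and Table 53 covers events that led to stopping treatment. The Exit Form reasons in 4.4 concern leaving the trial only.

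**Related provisions.** For a suspected allergic contact reaction, Protocol 8.2.3 stops the product and allows it to be resumed after a negative re-challenge. Section 8.2.1 follows treatment-related events until they resolve or stabilise. SAP 6.5.1.1 and Table 41 use a date of last use for each product.

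**The concern.** The primary question concerns Week 12 in all randomised subjects, but for a subject who exits early the plan collects a count on the day of leaving and uses it as the Week 12 value. Once the visits are missed, no later analysis can recover the Week 12 count.

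The arms differ only in the capsule, so capsule-related stopping may be unequal. If it is, part of a difference in tolerability can show up as a difference in lesion counts, or mask one. PP does not test this, because it may exclude the same subjects.

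**Working it through.** **1. The plan's own figures.** Inputs: difference 15 points and SD 35 (Protocol 9.2.1), 90% power (9.2.2), two-sided 0.05 (SAP 6).

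- n per group = 2 × [35 × (1.960 + 1.2816) / 15]² = 114.4. The plan has 114, which gives 89.9% power.
- Allowance: 114 / 0.85 = 134.1, so 135 per group, as stated.
- With Week 12 counts on all 135 per group and a 15-point difference: SE = 35 × √(2/135) = 4.26, power 94.1%.

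Like the plan's own calculation, these treat the endpoint as a difference in means. The planned test is rank-based and stratified by centre.

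**2. Where a leaver's count goes.**

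| Exit | Early termination count entered on | Week 12 value in ITT/LOCF |
|---|---|---|
| Before Week 4 | Week 4 pages | That count, carried forward |
| Between Weeks 4 and 8 | Week 8 pages | That count, carried forward |
| After Week 8 | Week 12 pages | That count, which may not be flagged as early |
| No termination visit attended | None | Last earlier count, or baseline (0% change) |

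**3. Unequal exits.** Let a and c be the exit rates (combination, control) and g the points by which the last count falls short of the subject's own Week 12 value. All three are assumed.

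- Shift in the difference = -(a - c) × g.
- SD in an arm with exit rate d = √[35² + d(1 - d)g²].

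The table takes the difference with complete Week 12 counts as 15 points for power, and as zero for the chance of falsely favouring the combination (2.5% without a shift).

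| Exits, combination vs control | g | Shift | Power | False favour |
|---|---|---|---|---|
| 10% vs 5% | 15 to 30 | -0.75 to -1.5 | 91.4% to 87.1% | below 2.5% |
| 15% vs 5% | 15 to 30 | -1.5 to -3.0 | 88.2% to 77.9% | below 2.5% |
| 5% vs 10% | 15 to 30 | +0.75 to +1.5 | above 94.1% | 3.7% to 5.3% |
| 5% vs 15% | 15 to 30 | +1.5 to +3.0 | above 94.1% | 5.4% to 10.1% |

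Worked row, 15% vs 5% with g = 30: SE = √[(1339.75 + 1267.75)/135] = 4.395. The difference is 15 - 3 = 12. Then 12/4.395 - 1.96 = 0.77, which gives 77.9% power.

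If counts worsen after the stop, g is negative and every sign reverses.

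**4. Equal exits.** An equal shortfall in both arms cancels. The difference is diluted only if the last count shows a fraction f of the 15-point benefit: 15 × [1 - d(1 - f)]. At d = 15% this runs from 12.75 (f = 0, power 84.9%) to 15 (f = 1, power 94.1%).

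**5. What follow-up would recover.** Take 75% on control (Protocol 2.1) and 90% on the combination (75 plus the assumed 15). Assume that leavers stop the capsule, keep ivermectin and reach 75% at Week 12, and that LOCF would instead carry a reduction e of 30 to 60.

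- 15% in both arms. With follow-up: 0.85 × 90 + 0.15 × 75 - 75 = 12.75. LOCF: 0.85 × (90 - 75) = 12.75. No gap.
- 20% vs 10%. With follow-up: 0.80 × 90 + 0.20 × 75 - 75 = 12.0. LOCF: (72 + 0.2e) - (67.5 + 0.1e) = 4.5 + 0.1e, or 7.5 to 10.5. The gap is 1.5 to 4.5 points, which agrees with the step 3 formula for g = 75 - e = 15 to 45.

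**The case against.** The strongest reply is that Protocol 7.2.1 only says which forms to complete and does not oblige anyone who stops a product to leave. That is true of the sentence. But 4.4 makes the Exit Form a record of leaving the trial, and nothing schedules a count afterwards, so the gap stands.

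Several stronger readings are tempting, and the documents do not support them:

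- **A reader might infer that every adverse-event stop ends contact.** Section 8.2.3 allows a stop followed by resumption, 8.2.1 continues follow-up of related events, and 4.3.5 provides for discussing whether a subject who needs prohibited therapy continues. None of these schedules a Week 12 count after a permanent stop.
- **A reader might infer that an early count always understates improvement in a steadily improving disease.** Section 2.1 gives ivermectin results as "76% and 75% versus 50% for both vehicle groups, respectively" and a doxycycline difference from placebo from week 3. It gives no visit-by-visit course, and counts could worsen after a stop.
- **A reader might apply the point to about 40 of 270 subjects.** The allowance (0.15 × 270 = 40.5) covers every exclusion: "To allow a 15% rate of subjects excluded from analysis (drop out, lost to follow-up, etc.) at Week 12, 135 subjects per group". No share is given for adverse events, and follow-up cannot recover subjects who are lost or withdraw consent.
- **A reader might measure the harm against 15 points.** Step 5 shows that off-treatment counts need not restore 15. With equal exits they may give the same result as LOCF.

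It is also fair to say that more exits on doxycycline would usually work against the superiority claim, that a last-use date per product is already planned, and that later counts may reflect other therapy, because 4.4 has leavers receive appropriate treatment. These points limit the size of the problem but do not supply the missing counts.

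**Conclusion.** The point holds in a limited form. A permanent adverse-event discontinuation is handled as trial exit, no Week 12 count follows, and an earlier count stands in for it in the primary analysis. After Week 8 that count can sit in the Week 12 field itself. PP is the only check, and it may exclude the same subjects.

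The direction of bias is not fixed. With exits differing by 10 percentage points and last counts 15 to 30 points short, the difference moves by 1.5 to 3.0 points either way, against a planned 15. With a 5-point imbalance it moves by 0.75 to 1.5. Equal exits mainly dilute the difference, and that dilution cannot be counted as a cost of missing follow-up. All exit rates and shortfalls here are assumptions.

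The sample size is not in question. This is an inexpensive improvement in which data are collected.

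**What to change.** - **Protocol 4.4, 5.5.2 and 7.2.1:** separate permanent discontinuation of a product from withdrawal from the trial. Subjects who stop a product but do not withdraw consent attend the remaining scheduled visits, at minimum for the Week 12 lesion count and IGA, with any new rosacea therapy recorded. Complete the Exit Form only when visits end. This says nothing about when product should be stopped or what treatment should follow.
- **Protocol 4.4 and the eCRF:** enter early termination counts under their actual date, so that they are not read as Week 12 values.
- **SAP:** use the last-use date per product already planned in 6.5.1.1 to mark stopping, and align Tables 2.1, 2.2 and 53 with the two concepts. Keep the primary analysis as planned and add one supportive ITT analysis using the collected Week 12 counts.

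**Cost:** protocol and eCRF wording, one more analysis, and attendance at visits already on the flow chart (5.4). The documents give no cost per visit. Some of the added counts will be taken on other therapy, which is why the analysis is supportive. Subjects who withdraw consent or are lost remain unrecovered.
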